1. STUDY PROTOCOL

1.1. Objective and Study Design

This is a prospective, observational study designed to evaluate the impact of preoperative anxiety on postoperative early recovery parameters, pain intensity, and the development of emergence delirium in pediatric patients.

1.2. Ethical Approval and Consent

The study protocol was approved by the Clinical Research Ethics Committee of University of Health Sciences, [name] Uz Children's Hospital (Date: April 24, 2025; Protocol No: GOA-155). The study was conducted in accordance with the Declaration of Helsinki. Written informed consent was obtained from the legal guardians of all participants prior to surgery.

1.3. Participant Selection

- **Inclusion Criteria:** Pediatric patients aged 2–7 years, classified as ASA (American Society of Anesthesiologists) physical status I–II, undergoing elective urogenital surgery under general anesthesia.
- **Exclusion Criteria:** Children with cognitive or mental developmental delays, diagnosed neurological or psychiatric disorders, chronic pain syndromes, or those undergoing emergency surgery. Cases involving experimental drugs or non-standard analgesia techniques were also excluded.

1.4. Anesthesia Management

A standardized general anesthesia protocol was applied to all participants:

- **Premedication:** No pharmacological premedication was administered.
- **Induction:** 0.1 mg/kg midazolam and 1 mcg/kg fentanyl. Airway was secured with a laryngeal mask airway (LMA) suitable for the child's weight.
- **Maintenance:** Inhalation anesthesia using sevoflurane and an air-oxygen mixture. Anesthesia depth was maintained at standard MAC values (1.0–1.2).
- **Postoperative Analgesia:** Standardized with 10 mg/kg paracetamol based on the surgical procedure and body weight.

1.5. Assessment and Data Collection

- **Preoperative Assessment:** Anxiety levels were assessed immediately before anesthesia induction using the Modified Yale Preoperative Anxiety Scale (mYPAS). Scores range from 23 to 100, with ge 30 indicating clinically significant anxiety.

- **Postoperative Assessment:** Conducted in the Post-Anesthesia Care Unit (PACU) at 0, 15, 30, 45, and 60 minutes:
 - **Pain Intensity:** Measured using the FLACC (Face, Legs, Activity, Cry, Consolability) scale (0–10).
 - **Emergence Delirium:** Monitored using the Pediatric Anesthesia Emergence Delirium (PAED) scale. Scores ≥ 10 indicated clinically significant delirium.
 - **Recovery Quality:** Evaluated using the Modified Aldrete Score (0–10).

2. STATISTICAL ANALYSIS PLAN (SAP)

2.1. Sample Size and Power Analysis

Sample size was determined based on the positive correlation coefficient ($r = 0.479$, $P = 0.001$) between preoperative anxiety and postoperative pain scores reported in the literature. With a Type I error rate (α) of 0.05 and a power (1-beta) of 0.95, the minimum required sample size was calculated as 51 patients. The study was completed with 114 patients to account for potential data loss and clinical variations.

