2.2. Statistical Methodology

- **Data Distribution:** Assessed using the Shapiro-Wilk test.
- **Descriptive Statistics:** Continuous variables are presented as Mean \pm Standard Deviation or Median (Interquartile Range). Categorical variables are presented as frequencies and percentages (n, %).
- **Comparative Analysis:** * Independent samples t-test, Pearson Chi-square, or Fisher's Exact tests were used for demographic and clinical comparisons.
 - The Mann-Whitney U test was applied for comparing PAED, FLACC, and Aldrete scores between groups (mYPAS < 30 vs. mYPAS ≥ 30).
- **Risk Analysis:** Raw Odds Ratios (OR) and 95% Confidence Intervals (CI) were calculated for clinical risk assessments at specific time points.
- **Regression Modeling:** Multivariate Logistic Regression analysis using the "Enter" method was performed to determine the independent effect of preoperative anxiety on outcomes. Models were adjusted for age, sex, ASA score, surgical history, and surgery type.
- **Significance Level:** $p < 0.05$ was considered statistically significant for all analyses.

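### The 51-patient minimum for 95% power belongs to a correlation test that section 2.2 does not list, and at that size it does not carry over to the analyses that are listed

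*Combined protocol and SAP*

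**What the plan says.** The planning effect is given in section 2.1: "Sample size was determined based on the positive correlation coefficient ($r = 0.479$, $P = 0.001$) between preoperative anxiety and postoperative pain scores". The error rate and power follow, "With a Type I error rate (α) of 0.05" and "power (1-beta) of 0.95, the minimum required sample size was calculated as 51 patients", without saying whether the test is one- or two-sided. The same section then reports the final size: "The study was completed with 114 patients to account for potential data loss and clinical variations".

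Section 2.2 sets out the analysis. For the three postoperative scales it says: "The Mann-Whitney U test was applied for comparing PAED, FLACC, and Aldrete scores between groups (mYPAS < 30 vs. mYPAS ≥ 30". It adds t-tests and chi-square or Fisher tests for demographic and clinical comparisons, unadjusted odds ratios with 95% confidence intervals at specific time points, and a logistic regression for the independent effect of anxiety, of which it says: "Models were adjusted for age, sex, ASA score, surgical history, and surgery type". It does not say whether mYPAS enters that regression as a score or as a two-level variable.

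The cut-off comes from section 1.5: "Scores range from 23 to 100, with ge 30 indicating clinically significant anxiety". Section 1.5 also gives a cut-off for PAED (10 or more) but none for FLACC. Section 1.1 names early recovery, pain and emergence delirium together as objectives.

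**The concern.** The plan's only power statement is for an analysis that the plan does not contain. Splitting mYPAS at 30 discards information, so a comparison of the two groups needs more patients than a correlation test to detect the same underlying association. Making the outcome binary as well, as the odds ratios and logistic regression do, costs more again. The planning correlation concerns pain only, so it gives nothing for delirium or recovery.

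If 0.95 is read as a property of the listed analyses, 51 looks like an adequate size for them, and a null result for delirium or recovery could be taken as stronger evidence of no association than the design supports.

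**Working it through.** **Inputs from the documents.** r = 0.479, α = 0.05, power 0.95, stated minimum 51, completed N = 114 (section 2.1); cut-off mYPAS 30 (section 1.5); tests and adjustment variables (section 2.2).

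**Assumptions, because the documents give no figure.** Bivariate normal scores; share of patients at mYPAS 30 or above; event rate of a binary pain outcome; adjustment variables independent of anxiety; no ties.

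**1. The plan's own figure.** Fisher z, two-sided:

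N = ((1.960 + 1.645) / atanh(0.479))² + 3 = (3.605 / 0.5217)² + 3 = 50.75, so 51.

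Power at 51 = Φ(0.5217 × √48 − 1.960) = 0.951. A one-sided test would need 43. The stated 51 is therefore the two-sided test of a continuous correlation, and it reproduces exactly.

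**2. Size needed once mYPAS is split.** Splitting a normal score with share p in one group multiplies r by φ(z_p) / √(p(1 − p)). Put the reduced r into the formula above, then divide the unrounded N by 3/π = 0.955, the large-sample efficiency of Mann-Whitney against the t-test for normal data.

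| Split | Factor | Reduced r | N before Mann-Whitney adjustment | N for 95% power, Mann-Whitney |
|---|---|---|---|---|
| 50/50 | 0.798 | 0.382 | 83.2 | 88 |
| 70/30 | 0.759 | 0.363 | 92.6 | 97 |
| 80/20 | 0.700 | 0.335 | 109.8 | 116 |
| 90/10 | 0.585 | 0.280 | 159.8 | 168 |

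**3. Power of the Mann-Whitney test on FLACC, by direct simulation** (repeat runs agree to about 0.01):

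| Split | n = 51 | N = 114 |
|---|---|---|
| 50/50 | 0.79 | 0.99 |
| 70/30 | 0.74 | 0.98 |
| 80/20 | 0.66 | 0.95 |
| 90/10 | 0.48 | 0.84 |

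At 80/20, the simulated 0.95 at 114 and the approximate requirement of 116 agree within the accuracy of the method.

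**4. Adjusted logistic regression** (Wald test, five independent covariates, pain made binary), simulated power at N = 114:

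| Event rate | mYPAS continuous | Binary, 30% anxious | Binary, 50% anxious | Binary, 70% anxious |
|---|---|---|---|---|
| 20% | 0.96 | 0.83 | 0.81 | 0.55 |
| 30% | 0.98 | 0.88 | 0.90 | 0.78 |
| 50% | 0.99 | 0.89 | 0.94 | 0.90 |

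Allowing for simulation error, the continuous coding gives about 0.95 to 0.99 and the binary coding about 0.55 to 0.94. With continuous mYPAS and only 10% events, power falls to about 0.84. At n = 51 the ranges over the same event rates are 0.61 to 0.79 (continuous) and 0.07 to 0.60 (binary).

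**5. Delirium and recovery.** No planning effect for PAED or Aldrete is given, so power cannot be computed. A detectable odds ratio can be computed only by assuming the anxious share and the event rate. For an unadjusted comparison at N = 114 with 80% power and 10%, 20% or 30% events in the low-anxiety group, it is about 4.2, 3.3 or 3.0 with 60% anxious. Over the same event rates it runs from 3.8 to 5.6 with 80% anxious and from 5.7 to 8.7 with 90% anxious.

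**The case against.** The strongest reply is that 51 is only a floor and the study finished with 114, a factor of 114 / 51 = 2.2 above it. At 114 the two-group FLACC test reaches about 0.95 or better for every split up to 80/20. Section 2.1 ties its power figure to anxiety and pain and claims none for delirium or recovery. The mismatch biases no estimate and invalidates no test. All of this stands, and it limits the point.

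Four stronger readings are tempting, and the documents do not support them:

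- *The planned analyses as carried out lack 95% power.* For the FLACC comparison at 114 this is true only if the split is very uneven, and the split is not given.
- *The logistic models fall short even at 114.* That holds for binary mYPAS in every case tried. Section 2.2 applies the cut-off of 30 to the Mann-Whitney groups and leaves the regression coding open; continuous coding gives about 0.95 to 0.99 at 20% to 50% events.
- *The calculation is wrong.* It is not; 51 reproduces exactly.
- *The reason given for 114 is false, because absorbing the excess by data loss alone would take a loss of 1 − 51/114 = 55%.* Section 2.1 also cites clinical variation. The reason is unquantified, but enrolling above a minimum is not an error.

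The reply does not rescue 51 as the minimum for the listed tests. Nor does it supply a power basis for the odds ratio, logistic, PAED or Aldrete analyses.

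**Conclusion.** The point holds as a mismatch between the basis of the sample size and the planned analyses. The pairing of 51 patients with 95% power is valid only for a two-sided test of a continuous anxiety–pain correlation of 0.479. At 51, none of the listed pain analyses examined reached 95% under any split or event rate tried; the best case was about 0.79. At the completed 114, the FLACC comparison is adequately powered unless about nine patients in ten fall on one side of the cut-off. The logistic result depends on a coding that the plan does not state.

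These sizes rest on bivariate normality, the planning correlation being true, and assumed splits and event rates. They describe a single test with no allowance for several time points and scales. FLACC ties, or adjustment variables correlated with anxiety, would lower them. The logistic figures also suppose a binary pain outcome, for which section 1.5 gives no FLACC cut-off.

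This should be corrected, but it is a reporting fault of moderate weight and does not threaten the validity of the study.

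**What to change.** In section 2.1:

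- State that 51 patients and 0.95 power apply only to a two-sided test of the continuous anxiety–pain correlation.
- Restate power for the two-group FLACC test at N = 114, using the planning correlation of 0.479 and the observed group split, not the observed effect.
- Say that the odds ratio, logistic, PAED and Aldrete analyses were not powered and should be read from their confidence intervals.
- Give no fixed detectable odds ratio unless the assumed anxious share and event rate are stated with a range.

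In section 2.2:

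- Enter mYPAS as a continuous score in the regression, or report that version beside the binary one, and state which coding each result uses.
- If a continuous mYPAS–FLACC correlation is added to match the sample size, label it as added after completion, since section 2.1 describes the study as completed.

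No extra patients are needed. The cost is redrafting, at most one additional model or correlation, and a power statement that looks less favourable than the present one.

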2.2. Statistical Methodology

- **Data Distribution:** Assessed using the Shapiro-Wilk test.
- **Descriptive Statistics:** Continuous variables are presented as Mean \pm Standard Deviation or Median (Interquartile Range). Categorical variables are presented as frequencies and percentages (n, %).
- **Comparative Analysis:** * Independent samples t-test, Pearson Chi-square, or Fisher's Exact tests were used for demographic and clinical comparisons.
 - The Mann-Whitney U test was applied for comparing PAED, FLACC, and Aldrete scores between groups (mYPAS < 30 vs. mYPAS ≥ 30).
- **Risk Analysis:** Raw Odds Ratios (OR) and 95% Confidence Intervals (CI) were calculated for clinical risk assessments at specific time points.
- **Regression Modeling:** Multivariate Logistic Regression analysis using the "Enter" method was performed to determine the independent effect of preoperative anxiety on outcomes. Models were adjusted for age, sex, ASA score, surgical history, and surgery type.
- **Significance Level:** $p < 0.05$ was considered statistically significant for all analyses.

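### FLACC, PAED and Aldrete scores are compared only by unadjusted tests: the sole adjusted method needs a yes/no outcome, and only PAED has a cut-off

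*Combined protocol and SAP*

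**What the plan says.** Section 1.1 sets the design and aim: "This is a prospective, observational study designed to evaluate the impact of preoperative anxiety" on recovery, pain and emergence delirium. Under section 1.3 the children are "Pediatric patients aged 2–7 years" having elective urogenital surgery.

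Section 1.5 schedules the outcome scales as "Conducted in the Post-Anesthesia Care Unit (PACU) at 0, 15, 30, 45, and 60 minutes". For PAED it adds "Scores ≥ 10 indicated clinically significant delirium". For FLACC and Aldrete it gives the 0–10 range and no cut-off.

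Section 2.2 then has three layers of outcome analysis:

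- Scores: "The Mann-Whitney U test was applied for comparing PAED, FLACC, and Aldrete scores between groups", the groups being mYPAS below 30 and 30 or above.
- Unadjusted risk: "Raw Odds Ratios (OR) and 95% Confidence Intervals (CI) were calculated for clinical risk assessments at specific time points".
- Adjusted risk: multivariable logistic regression, which "was performed to determine the independent effect of preoperative anxiety on outcomes". On covariates: "Models were adjusted for age, sex, ASA score, surgical history, and surgery type".

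The SAP does not say which outcomes, cut-offs or time points enter the logistic models. It labels no analysis as primary, and it describes no repeated-measures method.

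**The concern.** Anxiety is observed, not assigned. Children above and below mYPAS 30 may differ in age and operation, and both may affect pain, agitation and recovery scores. By listing age, sex, ASA score, surgical history and surgery type as adjustment factors, the SAP accepts that such differences matter.

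A Mann-Whitney test takes no covariates and a raw odds ratio has none by definition. The one adjusted method needs a binary outcome. For FLACC and Aldrete this leaves two possibilities: the score gets an unadjusted test only, or it is dichotomised at a value the plan does not state. Neither supports a conclusion about the effect of anxiety on the score itself. Pain is affected most, because section 2.1 sizes the study on the correlation between anxiety and pain scores.

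Each child also contributes five assessments, and no described method combines them or accounts for their correlation.

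**Working it through.** **1. The plan's own figure.** Inputs from section 2.1: r = 0.479, α = 0.05, power 0.95. The two-sided Fisher z formula is n = ((z₀.₉₇₅ + z₀.₉₅) / atanh r)² + 3 = ((1.960 + 1.645) / 0.5217)² + 3 = 50.75, so 51. The stated minimum reproduces. At n = 114, power for the same r is Φ(0.5217 × √111 − 1.960) = Φ(3.54), above 0.999. The issue is therefore not a shortage of patients for the planned correlation. It is what the comparisons estimate.

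**2. Which outcome has which analysis.**

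| Outcome | Score analysis | Stated cut-off | Adjusted analysis that can be carried out as written |
|---|---|---|---|
| PAED | Mann-Whitney, unadjusted | ≥ 10 | Logistic on PAED ≥ 10, time point not stated |
| FLACC (pain) | Mann-Whitney, unadjusted | none | none without choosing a cut-off |
| Aldrete (recovery) | Mann-Whitney, unadjusted | none | none without choosing a cut-off |

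No row has an adjusted analysis of the score or a method for repeated measures.

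**3. How far an unadjusted score test could mislead.** The documents give no correlation of age with mYPAS or with any score, so the values here are assumptions. Let age correlate c with both mYPAS and the score, with no effect of anxiety. All variables are taken as normal, n = 114, and one two-sided test is made at 0.05. mYPAS and the score then correlate c × c through age alone.

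The expected Mann-Whitney z is approximately c² × k × √114 × √(3/π). Here k = φ(q) / √(p(1 − p)), p is the share of children in one group, and q is the matching normal quantile. Equal groups give k = 0.798. A 15/85 split (17 and 97 children) gives k = 0.652.

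Example with c = 0.4 and equal groups: 0.16 × 0.798 × 10.68 × 0.977 = 1.33. The rejection probability is Φ(1.33 − 1.96) + Φ(−1.33 − 1.96) = 0.265.

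| c | Equal groups: formula | Equal groups: simulation | 15/85: formula | 15/85: simulation |
|---|---|---|---|---|
| 0.2 | 0.063 | about 0.06 | 0.059 | about 0.06 |
| 0.3 | 0.116 | about 0.12 | 0.094 | about 0.10 |
| 0.4 | 0.265 | about 0.26 | 0.193 | about 0.18 |
| 0.5 | 0.548 | about 0.54 | 0.398 | about 0.41 |

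Repeat simulation runs differ by one or two percentage points. At c = 0.2 there is almost no inflation; at 0.4 and above it is large.

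**4. Raw odds ratios.** This is again an illustration with assumed values: true odds ratio 1, baseline risk 20%, and one binary confounder. Suppose the confounder has odds ratio 3 and is present in 70% of one group and 30% of the other. Risk with the confounder is 0.75 / 1.75 = 0.429. Group risks are 0.7 × 0.429 + 0.3 × 0.2 = 0.360 and 0.3 × 0.429 + 0.7 × 0.2 = 0.269. The raw odds ratio is (0.360/0.640) / (0.269/0.731) = 1.53. For confounder odds ratios of 1.5 to 3, the raw odds ratio runs from 1.18 to 1.53 at 70% against 30%, and from 1.08 to 1.24 at 60% against 40%.

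**The case against.** The strongest reply is that the SAP already adjusts. Its logistic models contain all five covariates, age and surgery type included, and they are the analysis given the task of estimating the independent effect. That stands, and it rules out three stronger readings a reader might infer:

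- *That confounding passes into the study's main results.* The SAP calls no analysis main or primary, and the analysis meant to isolate anxiety is adjusted. The documents support only that the score comparisons and raw odds ratios are unadjusted.
- *That a FLACC or Aldrete cut-off was picked after seeing the data.* None is stated, and section 2.1 reports the study as completed. That leaves the risk open; it does not show that a cut-off was used, or when it was chosen.
- *That the Mann-Whitney test was run separately at each of the five times.* This is plausible, but section 2.2 refers to time points only for the odds ratios. What can be read from the text is that no longitudinal method is described.

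It is also fair to say that the illustration rests on assumed correlations of equal strength on both sides, that weak confounding (0.2) does almost no harm, and that unequal groups reduce the inflation. A model added now is itself a choice made after completion and must be reported as such.

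The gap survives these replies. Adjusted logistic regression cannot serve a 0–10 score that has no stated cut-off.

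**Conclusion.** The point holds in this form. The score comparisons for all three scales and the raw odds ratios are unadjusted in an observational study whose SAP names five covariates. Pain and recovery have no adjusted analysis on their scores, PAED has one only as a yes/no outcome, and the repeated assessments are not used together.

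The gaps can be read directly from sections 1.5 and 2.2. Their numerical consequence cannot. It ranges from negligible to a rejection rate of about one in two, depending on confounding strengths and group sizes that the documents do not give. The change is worth making because it is cheap, but nothing here shows that a reported result is wrong.

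**What to change.** For each of FLACC, PAED and Aldrete, add one covariate-adjusted repeated-measures model on the full score.

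- **Form:** fix it in writing before the model is run, for example an ordinal mixed model with a random intercept per child.
- **Terms:** mYPAS group (below 30 against 30 or above, as in the SAP), time, mYPAS group × time, age, sex, ASA class, surgical history and surgery type.
- **Reporting:** give the average mYPAS effect over 0–60 minutes together with the effect at each time, so that an early effect is not hidden by averaging.
- **Role:** base conclusions about the impact of anxiety on the scores on this model. Label the Mann-Whitney tests and raw odds ratios as descriptive.
- **Logistic model:** keep the adjusted model for PAED ≥ 10, and state the time point or points it uses.
- **Transparency:** state that the repeated-measures models were added after the study was completed.

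The models need no FLACC or Aldrete cut-off and can include children who missed an assessment. The cost is SAP wording and modest extra analysis on data already collected. The drawbacks are that results depend on the model, and that confounding by unmeasured factors remains.

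### No between-group estimate with a confidence interval is specified for FLACC or Aldrete scores (or for PAED as a score), so the size and precision of the association of anxiety with pain and recovery would go unreported

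*Combined protocol and SAP*

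**What the plan says.** Section 1.1 describes a prospective observational study and asks about the impact of preoperative anxiety on "postoperative early recovery parameters, pain intensity, and the development of emergence delirium". Under section 1.5 the postoperative assessments are "Conducted in the Post-Anesthesia Care Unit (PACU) at 0, 15, 30, 45, and 60 minutes". FLACC and Aldrete are each given as 0–10 scales. PAED has a cut-off of 10 for clinically significant delirium. No cut-off is given for FLACC or Aldrete.

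Section 2.2 contains four elements that bear on these scores:
- **Descriptive summaries:** mean with SD, or median with IQR. The text does not say that they are given by anxiety group or by time point.
- **Group comparison of the scores:** "The Mann-Whitney U test was applied for comparing PAED, FLACC, and Aldrete scores between groups".
- **Risk analysis:** "Raw Odds Ratios (OR) and 95% Confidence Intervals (CI) were calculated for clinical risk assessments at specific time points". The endpoints are not named.
- **Adjusted analysis:** logistic regression with age, sex, ASA score, surgical history and surgery type as covariates, for outcomes that are not named.

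A p-value below 0.05 "was considered statistically significant for all analyses".

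**The concern.** The objective concerns pain intensity and quality of recovery, and on ordered scales that is a question of size. A Mann-Whitney p-value does not answer it. If the result is significant, the reader is not told how far apart the groups are. If it is not, the reader cannot tell a small difference from a worthwhile one that was estimated too imprecisely to detect.

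The Mann-Whitney test is also not a test of medians. It compares whole distributions, through how often a child in one group outscores a child in the other. On a 0–10 scale with many tied values, two groups can share a median and still give a small p-value. That is a property of the test, not an error. It matters here because no measure matching the test is planned, so the median and IQR may be the only description of size a reader sees.

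The sample size was built on a correlation, which is an effect size. No correlation, linear or ordinal analysis of the scores is listed, so the result could not be set beside the planning assumption either.

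**Working it through.** **1. The plan's own figure (SAP 2.1).** Inputs: r = 0.479, α = 0.05 (taken as two-sided), power 0.95. Fisher z formula: n = ((1.960 + 1.645)/atanh(0.479))² + 3, with atanh(0.479) = 0.5217. This gives (3.605/0.5217)² + 3 = 50.75, rounded up to 51. The stated 51 is reproduced, and the point below does not disturb it.

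**2. Which outcomes have an interval.** Setting sections 1.5 and 2.2 side by side:
- *Delirium as an event (PAED ≥10):* the cut-off is stated, so odds ratios with 95% CIs plausibly apply.
- *PAED as a score:* Mann-Whitney only.
- *FLACC:* Mann-Whitney only; no cut-off is stated that would make it binary.
- *Aldrete:* the same as FLACC.

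Logistic regression does not fill the gap, because it too needs a binary outcome.

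**3. What p<0.05 corresponds to at N = 114.** The test measures the probability of superiority, U/(n₁n₂) with ties counted half, which is 0.5 under no association. Without ties, the critical value is 0.5 + 1.96·√((n₁+n₂+1)/(12·n₁·n₂)). The documents do not give the group split, so two are assumed.
- 57/57: 0.5 + 1.96·√(115/38,988) = 0.5 + 0.106 = 0.606.
- 85/29: 0.5 + 1.96·√(115/29,580) = 0.5 + 0.122 = 0.622.

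For a score expected to be lower in anxious children, the mirror values are 0.394 and 0.378. For normal-shaped scores, 0.606 corresponds to about 0.38 SD and 0.622 to about 0.44 SD.

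**4. Precision the missing intervals would show.** By the same formula, the approximate 95% half-width for the probability of superiority near the null is ±0.106 with half the children in the smaller group, ±0.109 with 40%, ±0.116 with 30% and ±0.133 with 20%. These shares are assumed. The width is enough to matter when a non-significant result is interpreted.

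**5. Can medians and p-value disagree?** Constructed scores, 57 per group:
- Lower anxiety: 40 zeros, 10 ones, 7 twos.
- Higher anxiety: 29 zeros, 4 ones, 8 threes, 8 fours, 8 fives.

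Both medians are 0, with IQRs 0–1 and 0–4. U = 29·40/2 + 4·(40 + 10/2) + 24·57 = 580 + 180 + 1,368 = 2,128, and 2,128/3,249 = 0.65. The tie-corrected p is 0.0012. The means are 24/57 = 0.42 and 100/57 = 1.75, a difference of 1.33 points. The Hodges-Lehmann shift is 0 (95% CI 0 to 2), so on tied data that estimate alone would also understate the difference.

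**6. How often would this happen?** No figure can be given. In simulations (1,500 runs per setting; rounded, truncated normal scores; shifts of 0.3–0.7 SD; both splits above), an Aldrete-like score with 40% at the ceiling had equal medians in 84–95% of significant results at an assumed SD of 0.7, 50–85% at SD 1.0 and 3–35% at SD 1.5. For a FLACC-like score (mean 0–3, SD 2–2.5) it was 1–13%. The bounds move by a few points on re-running. The spread comes from the assumed distributions, and the documents contain none.

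**The case against.** The strongest reply is that section 2.2 is not a p-value-only plan. It provides group-type summaries, and a mean and SD with group sizes let a reader construct a difference and an interval. It plans raw odds ratios with 95% CIs at time points, and adjusted models. Delirium is phrased in the objective as something that develops, it has a cut-off, and it is plausibly served by those odds ratios. All of this stands, so a reader should not infer that nothing quantitative is planned, or that delirium is left without an estimate.

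Three further inferences are tempting and unsupported:
- *That significance is the sole rule for conclusions.* Section 2.2 sets a 0.05 level; it does not say that conclusions rest on p alone.
- *That trivially small shifts would be called significant.* At N = 114 the threshold is about 0.38 to 0.44 SD for normal-shaped scores, which is not very small.
- *That equal medians with a significant test have occurred, or will usually occur.* The documents contain no results, and the frequency swings widely with the assumed distribution.

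The reply does not close the gap for FLACC and Aldrete. The summaries carry no interval for a difference, may be medians from which none can be built, and are not tied to group or time. The odds ratios need cut-offs that are not stated for these two scales.

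**Conclusion.** The point holds in a limited form. For FLACC and Aldrete, and for PAED treated as a score, no between-group estimate with a confidence interval is specified on the scale of the score. Two of the three parts of the objective, pain intensity and recovery, would therefore be reported without the size and precision of their association with anxiety. The stronger statement that the study cannot say how much anxiety changes any score does not follow. Descriptive summaries and odds ratios are planned, and an observational design supports association, not change.

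The size of the gap can be stated only under assumptions. With splits between 57/57 and 85/29 and no ties, significance requires a probability of superiority of about 0.606 to 0.622. Disagreement between medians and p-value is possible, as the constructed example shows, but its frequency is unknown. This is a cheap improvement to what the study can conclude. It does not invalidate the test or the sample size.

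**What to change.** Add to section 2.2, for FLACC and Aldrete (and PAED as a supporting score) at each of 0, 15, 30, 45 and 60 minutes:
- the probability that a child with mYPAS ≥30 scores higher than a child with mYPAS <30 (U/(n₁n₂), ties counted half) with a 95% CI;
- the difference in mean score with a bootstrap 95% CI;
- the Mann-Whitney p-value alongside.

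Label these as unadjusted associations. For the independent association, add a proportional-odds model of each score with the covariates section 2.2 already lists (age, sex, ASA score, surgical history, surgery type), reported with a 95% CI and a check of the proportional-odds assumption.

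Cost: the study is described as completed with 114 patients, so this means added analysis and reporting as well as SAP wording. It needs no new data and leaves N unchanged. The downside is volume: 3 scales × 5 times × 2 measures = 30 unadjusted intervals, plus the model estimates. No primary score or time is named in the documents, so the set should be presented and read as a whole.

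### The stated score comparisons use mYPAS only as below 30 versus 30 and above, and no listed analysis is stated to use the full score, which costs precision for effects smaller than the planning correlation

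*Combined protocol and SAP*

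**What the plan says.** Protocol section 1.5 records preoperative anxiety on the mYPAS ("Scores range from 23 to 100") and takes 30 or more as clinically significant anxiety. FLACC, PAED and Aldrete scores are taken at five time points in the PACU.

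SAP section 2.1 bases the sample size on a "positive correlation coefficient ($r = 0.479$, $P = 0.001$) between preoperative anxiety and postoperative pain scores". It gives an alpha of 0.05, "a power (1-beta) of 0.95", and says that "the minimum required sample size was calculated as 51 patients". It then reports that "The study was completed with 114 patients".

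SAP section 2.2 applies the Mann-Whitney test to PAED, FLACC and Aldrete scores "between groups (mYPAS < 30 vs. mYPAS ≥ 30". It also lists raw odds ratios at specific time points, and logistic regression for the independent effect of preoperative anxiety. For neither does it say whether mYPAS enters as a score or as two groups. It lists no correlation.

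**The concern.** The study was sized on an association that the plan never says it will estimate. The score comparisons reduce mYPAS to two groups, so a child at 31 is handled like a child at 100 and unlike a child at 29. The upper group runs from 30 to 100, which is 70 of the scale's 77 points.

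Three things are at stake:
- **Precision.** If outcomes change steadily with anxiety, a two-group comparison uses less of the data than an analysis of the score.
- **Dose-response.** Two groups cannot show whether outcomes worsen as anxiety rises. That bears directly on the objective in section 1.1.
- **Reproducibility of the adjusted analysis.** With the coding unstated, a reader cannot tell whether an adjusted odds ratio is per point, per some number of points, or for one group against the other.

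**Working it through.** **Inputs from the documents.** r = 0.479, alpha = 0.05, power = 0.95, stated minimum 51 and achieved N = 114 (section 2.1); scale 23–100 with the cut at 30 (section 1.5); Mann-Whitney on the two groups (section 2.2).

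**Assumptions, because the documents give no figure.** The share of children below 30 is taken as 50/50 to 10/90. The score is taken as roughly normal with a linear effect, then varied in step 4. The test is taken as two-sided.

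**Step 1: the plan's own figure.** With the Fisher z formula for one correlation, n = ((z₀.₉₇₅ + z₀.₉₅)/atanh(r))² + 3 = ((1.960 + 1.645)/0.5217)² + 3 = 50.75, so 51. The stated minimum reproduces (a one-sided test would give 43). This formula contains no split.

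**Step 2: efficiency of the split.** For a normal score cut so that a share p falls on one side, efficiency relative to the full score is φ(z_p)²/(p(1 − p)). At 50/50 this is 0.3989²/0.25 = 0.637; at 20/80 it is 0.2800²/0.16 = 0.490. Children lost = 114 × (1 − efficiency).

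**Step 3: consequence at the planning effect.** The correlation with the two-group variable is 0.479 × √efficiency. Putting this back into the Fisher z formula gives the N for 95% power. Power at N = 114 is Φ(√111 × atanh(r) − 1.960).

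| Split | Efficiency | Information lost | Children lost of 114 | N for 95% power | Power at N = 114 |
|---|---|---|---|---|---|
| Full score | 1 | 0% | 0 | 51 | >99.9% |
| 50/50 | 0.637 | 36% | 41 | 84 | 98.9% |
| 30/70 | 0.576 | 42% | 48 | 93 | 98.0% |
| 20/80 | 0.490 | 51% | 58 | 110 | 95.7% |
| 10/90 | 0.342 | 66% | 75 | 160 | 85.9% |

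Simulated Mann-Whitney power (4,000 replicates per split) agrees: 98.9%, 98.0%, 95.5% and 83.8%.

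**Step 4: other score distributions, effect still linear.** A uniform score split evenly loses about 29 children. Right-skewed scores (exponential, gamma, lognormal) with 20% of children below 30 lose about 80 to 90. With only 10% below 30 these skewed examples lose more still, about 97 to 103.

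**Step 5: smaller effects.** The smallest correlation that the full score detects with 80% power at N = 114 is tanh((1.960 + 0.842)/√111) = 0.26. At that value the step 3 formula gives the split about 60% (50/50), 49% (20/80) and 36% (10/90). By simulation at r = 0.25 with a 60/40 split, power is about 0.54 for Mann-Whitney on the groups and about 0.73 for Spearman on the score. Neither 0.25 nor 0.26 comes from the documents; they illustrate an effect about half the planning value.

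**The case against.** The strongest defence is that 30 is the threshold the protocol itself gives for clinically significant anxiety, so comparing children with and without it is a legitimate clinical question. That stands, and it is a reason to keep the comparison. It is not a reason to have no stated analysis of the score.

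A second defence is that the study is large enough anyway. At r = 0.479 this is right unless the split is very lopsided (step 3). But the planning figure concerns pain only. Delirium and Aldrete scores are tested too, over five time points, and their associations may be weaker.

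Third, the efficiency figures need a linear effect. If risk changes mainly at the threshold, the formula does not apply and the split may lose little. That also stands, and is why a check for non-linearity belongs with the score analysis.

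Three stronger readings are tempting and are not supported:
- **That the split discards most of the information.** Under normality the loss passes 50% only when the smaller group holds fewer than about 21% of children, and the documents do not give the split. That only 7 of 77 scale points lie below the cut describes the scale, not where the children fall.
- **That no analysis uses the actual score.** Section 2.2 ties the split explicitly only to the Mann-Whitney tests. mYPAS could be continuous in the logistic models.
- **That the split weakens adjustment for confounders.** mYPAS is the exposure here, and nothing computed shows such an effect.

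Section 2.1 also does not name the anxiety scale or the type of correlation behind 0.479. That it was a correlation on a full score is a reasonable inference, not a documented fact.

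**Conclusion.** The concern holds as a loss of precision and an unstated coding, not as a failure of the design. The mismatch between a sample size resting on a correlation and score comparisons resting on two groups is visible in the text and needs no assumption. The size of the loss does: a third or more of the information for a roughly normal score with a linear effect, rising as the split becomes uneven, with the split and distribution both unknown.

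A reader might infer that the study is underpowered for its planning effect. Under the same assumptions the documents' own figures point the other way for splits from 20/80 to 50/50. The practical cost is lower power for weaker associations, no view of a dose-response in the group comparisons, and a planning relation that is not stated to be estimated.

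**What to change.** In section 2.2:
1. State how mYPAS is coded in the raw odds ratios and in the logistic models.
2. Enter mYPAS as a continuous exposure in the logistic models, reported per 10 points, with one check for non-linearity such as a three-knot spline.
3. Report a correlation, for example Spearman's, of the mYPAS score with FLACC, and likewise with PAED and Aldrete, so that the relation used for planning is estimated.
4. Keep the comparison of below 30 with 30 and above as the clinical-threshold presentation, and report how many children fall on each side.
5. Because section 2.1 describes the study as completed, label the score analyses as added after data collection.

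The cost is SAP wording and a few extra analyses of data already held. The downside is that these additions are post hoc and have to be presented as such.
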